## **Study protocol**

### **Background**

Acute myocarditis is divided into fulminant or non-fulminant myocarditis depending on the presence or absence of hemodynamic stability. It is known that the prognosis of fulminant myocarditis is poorer than that of non-fulminant. In addition, additional research is needed on the risk factors contributing to the deterioration of the clinical course. In particular, studies on acute myocarditis published in renowned international journals have only been conducted with a small number of patients, ranging from dozens to hundreds of patients, so it is more necessary to conduct studies that include a large number of patients with public confidence on the overall clinical course and prognosis of myocarditis.

### **Objective**

In this study, we investigated the clinical characteristics of patients with acute myocarditis in Korea and sought to find out the treatment results and prognosis of fulminant myocarditis requiring vasopressors or mechanical assist devices.

### **Design**

Patients diagnosed with acute myocarditis from January 2004 to December 2021 at 6 domestic institutions were investigated for baseline characteristics and clinical course.

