#### 2) Observational data and Clinical test

##### (1) Observational data

- ① General characteristics: patient identification code, time of visit (year/month), age, sex, height, weight, vital signs upon admission, symptoms
- ② Underlying diseases: diabetes, hypertension, chronic kidney disease, coronary artery disease, peripheral vascular disease
- ③ Causes of myocarditis: Myocarditis caused by viral, giant cell, immune checkpoint inhibitors
- ④ Conservative treatment of myocarditis and treatment with immunosuppressants and vasopressors
- ⑤ ECMO treatment: date of insertion of ECMO, date of ECMO removal, whether or not venting is performed during ECMO maintenance, date of venting
- ⑥ Clinical results: in-hospital mortality, all-cause mortality, heart transplant, left ventricular assist device insertion, re-hospitalization

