## **Statistical Analysis Plan (SAP)**

All data for statistical test are analyzed using SPSS and R. All measurements for continuous variables are expressed as mean  $\pm$  standard deviation, and measurements for discrete variables are expressed as percentages. Student's t-test is used for comparative analysis of continuous variables, and  $\chi^2$ -test is used for comparison between two groups for discrete variables. After treatment for myocarditis, recovery of myocardial function and correlation with clinical results were analyzed using paired t test and Kaplan-Meier survival analysis. Predictors of death and factors requiring ECMO treatment were identified through binary logistic regression analysis. Binary logistic regression

analysis requires the occurrence of 10-15 events per independent variable, but in this study, about 30%, or about 270 people, are expected to die, so enough risk factors can be studied. The goodness of fit of the risk prediction model will be tested by C-statistic and Hosmer-Lemeshow tests. In addition, death or re-hospitalization during follow-up will be estimated by the Cox survival analysis method. After checking the fitness of the model by checking Schoenfeld's residual, the hazard of each risk factor is identified. A case of  $P < 0.05$  is considered statistically significant.

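### The SAP specifies no adjustment for institution or calendar period, although the cohort pools 6 hospitals over 18 years, so centre or era differences can appear as predictors of death or ECMO.

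*Combined protocol and SAP*

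**What the plan says.** The Design section covers cases diagnosed "from January 2004 to December 2021 at 6 domestic institutions". That is one pooled cohort from six hospitals over 18 calendar years (2021 − 2004 + 1).

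The SAP plans three sets of models:

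- Logistic regression for two outcomes: "Predictors of death and factors requiring ECMO treatment were identified through binary logistic regression analysis".
- Cox regression: "death or re-hospitalization during follow-up will be estimated by the Cox survival analysis method".
- A risk prediction model: "The goodness of fit of the risk prediction model will be tested by C-statistic and Hosmer-Lemeshow tests".

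For the size of the data it says that "about 30%, or about 270 people, are expected to die", and it asks for 10 to 15 events per independent variable.

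The SAP lists no covariates for any model. It does not mention an institution term, a calendar term, stratification, a random effect, frailty or a cluster-robust variance. The Observational data list includes "time of visit (year/month" among the general characteristics, but no section gives it a role in the analysis. Institution does not appear in that list.

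**The concern.** The Background section gives the need for work on risk factors as a motive for the study, and the SAP makes identified predictors an explicit output. Several listed data items could plausibly differ between hospitals or change over 18 years: myocarditis caused by immune checkpoint inhibitors, immunosuppressant treatment, ECMO and venting, NT-proBNP and cardiac MRI. Mortality could differ in the same way. A factor that was commoner in a high-mortality hospital or period would then be associated with death in the pooled data even if it had no effect within any hospital or period.

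The ECMO model is the most direct case. Receiving ECMO is a decision that can depend on local availability and on the year, so a hospital's or an era's practice can show up as a patient-level reason for needing it.

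The checks that the SAP names would not reveal this. The C-statistic measures discrimination, the Hosmer-Lemeshow test compares observed with predicted risk, and Schoenfeld residuals address proportional hazards. None looks for confounding by centre or era.

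**Working it through.** **Inputs from the documents.** 6 institutions; 18 years; about 270 deaths, about 30% of patients; 10 to 15 events per variable; significance at P < 0.05. The SAP does not state sidedness; two-sided is assumed here.

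**The plan's own figure.** No total sample size is stated, so 270 deaths cannot be reproduced independently. It implies 270 / 0.30 = 900 patients, or on average 900 / 6 = 150 patients and 270 / 6 = 45 deaths per institution.

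**Size of the possible bias.** The documents give no mortality or factor frequency by centre or era, so the following values are assumptions. Take 900 patients in three equal periods of 300, with no association between factor and death within any period (odds ratio 1.0). Pool the three tables and compute

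- OR = (a × d) / (b × c), where a and b are deaths and survivors with the factor, and c and d are deaths and survivors without it;
- SE of ln OR = √(1/a + 1/b + 1/c + 1/d);
- chance of P < 0.05 = Φ(|ln OR|/SE − 1.96) + Φ(−|ln OR|/SE − 1.96).

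First scenario in full. Mortality is 40/30/20% and factor frequency 20/40/60%.

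- With the factor: 60 + 120 + 180 = 360 patients and 24 + 36 + 36 = 96 deaths, so 264 survive.
- Without it: 240 + 180 + 120 = 540 patients and 96 + 54 + 24 = 174 deaths, so 366 survive.
- OR = (96 × 366) / (264 × 174) = 0.76; SE = 0.151; |ln OR|/SE = 1.78; chance of P < 0.05 = 43%.

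| Mortality by stratum (%) | Factor frequency (%) | Deaths with factor | Deaths without | Pooled OR | Chance of P < 0.05 |
|---|---|---|---|---|---|
| 40/30/20 | 20/40/60 | 96/360 | 174/540 | 0.76 | 43% |
| 40/30/20 | 60/40/20 | 120/360 | 150/540 | 1.30 | 43% |
| 35/30/25 | 20/40/60 | 102/360 | 168/540 | 0.88 | 14% |
| 35/30/25 | 30/40/50 | 105/360 | 165/540 | 0.94 | 7% |
| 30/30/30 | 20/40/60 | 108/360 | 162/540 | 1.00 | 5% |

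The last row shows the condition: if mortality does not vary across strata, the bias disappears. The same holds if the factor's frequency does not vary.

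**Check with six centres.** A simulation (900 patients, 6 centres, 18 years, 600 replicates per scenario) used a factor with no true effect. Its frequency varied by centre with SD 0.5 on the logit scale, in line with centre mortality. Where an era trend in mortality was set, the factor's frequency followed it too.

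| Between-centre SD, log-odds of death | Era trend (log-OR over the period) | Unadjusted: P < 0.05 | Unadjusted OR | With institution and three-period terms: P < 0.05 |
|---|---|---|---|---|
| 0 | none | 5% | 1.00 | 5% |
| 0.3 | none | 18% | 1.16 | 7% |
| 0.5 | none | 38% | 1.27 | 5% |
| 0.3 | −0.7 | 29% | 1.22 | 6% |
| 0.5 | −0.7 | 48% | 1.33 | 4% |

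A further run had centre SD 0.3 and era trend −0.7 but constant factor frequency. It gave 3% unadjusted and 4% adjusted.

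**Can the death model afford the terms?** The SAP's rule allows 270 / 15 = 18 to 270 / 10 = 27 parameters. Institution as fixed effects takes 5 and calendar time 1 or 2, together 6 or 7. That leaves between 18 − 7 = 11 and 27 − 6 = 21 for patient factors. The same check cannot be made for ECMO, because no expected number of ECMO cases is given.

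**The case against.** The strongest reply is that the SAP names no covariates at all, so the gap is one of non-specification. That stands. A reader might infer that the sponsor decided to treat the cohort as one homogeneous sample; the text is silent and does not support that. The point survives, because centre and period are features of how this sample was assembled, and nothing commits the analyst to include them.

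The 43% depends on assumed trends that are strong, monotone and perfectly aligned. That also stands: nothing in the documents suggests mortality halving while a factor's frequency triples, and the six-centre simulation also aligns centre mortality with factor frequency. Both are one-factor calculations. In a multivariable model, measured severity or treatment variables could absorb part of the centre or era effect.

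Two other inferences go further than the documents. The first is that institution is already recorded: only the visit date is listed. Institution may be recoverable from the source records, but no section says so. The second is that standard errors ignoring hospital are wrong. They may be, if residual between-hospital variation exists, but the documents do not show that it does, and the calculations above concern bias in the estimate.

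Finally, fixed institution terms suit a model meant to identify factors. In a prediction model judged by the C-statistic they can raise apparent discrimination through hospital identity, and they cannot be applied to a patient at a seventh hospital. This stands and limits where the terms belong.

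**Conclusion.** The concern holds in conditional form. As written, the SAP leaves its death, ECMO and Cox models without any specified adjustment for institution or calendar period. Where both outcome and factor frequency vary by centre or era, a factor with no effect can be reported as a predictor.

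Under the tabulated three-stratum assumptions with varying mortality, the false-positive rate is about 7% to 43% against a nominal 5%. It is near 5% if either condition fails. These figures show what could happen; they do not estimate what will happen in this cohort. They rest on the implied 900 patients, two-sided testing and the assumed trends. The change is worth making because it is cheap for the death model and removes a foreseeable source of false predictors.

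**What to change.** 1. **Observational data:** add institution as an explicit item. Year and month of visit are already collected.
2. **SAP, logistic models used to identify factors for death and for ECMO:** state that they adjust for institution and for calendar year of visit (linear or by period).
3. **SAP, Cox model:** state that it is stratified by institution and adjusted for calendar year.
4. **Reporting:** give the estimates without these terms alongside, so that readers can see how far each factor depends on them.
5. **Risk prediction model:** report the C-statistic and Hosmer-Lemeshow result without institution terms.

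**Cost.** One added data item and a few SAP sentences. In the death model the terms use about 6 to 7 of 18 to 27 parameters. Stratifying the Cox model by institution uses none; linear year uses one. For ECMO, the sponsor should first state the expected number of cases. If they are few, the most economical form is linear year with conditional or random-intercept adjustment for institution, noting that a random-intercept variance would be estimated from only 6 clusters.

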### **Method**

#### 1) Analysis method

- Review medical records and reanalyze previously performed blood tests, electrocardiograms, echo-cardiographic tests, imaging tests, and biopsies.
- Clinical results (in hospital mortality, death from any cause, heart transplantation, permanent left ventricular assist device insertion, hospitalization) and changes in echocardiographic findings of patients treated for myocarditis should be confirmed prior to the clinical trial approval date.

#### 2) Observational data and Clinical test

##### (1) Observational data

- ① General characteristics: patient identification code, time of visit (year/month), age, sex, height, weight, vital signs upon admission, symptoms
- ② Underlying diseases: diabetes, hypertension, chronic kidney disease, coronary artery disease, peripheral vascular disease
- ③ Causes of myocarditis: Myocarditis caused by viral, giant cell, immune checkpoint inhibitors
- ④ Conservative treatment of myocarditis and treatment with immunosuppressants and vasopressors
- ⑤ ECMO treatment: date of insertion of ECMO, date of ECMO removal, whether or not venting is performed during ECMO maintenance, date of venting
- ⑥ Clinical results: in-hospital mortality, all-cause mortality, heart transplant, left ventricular assist device insertion, re-hospitalization

## (2) Clinical test

- ① Laboratory test: cardiac enzyme, NT-proBNP, hemoglobin, platelet count, Aspartate Aminotransferase (AST), alanine aminotransferase (ALT), Blood Urea Nitrogen (BUN), Creatinine
- ② Cardiac echocardiography: LVEF, TAPSE, TV s', LV dimension, IVS thickness, LV posterior wall thickness, E flow, e velocity, RVSP, LAVI
- ③ Heart magnetic resonance imaging (MRI): presence of late gadolinium enhancement, edema

## **Statistical Analysis Plan (SAP)**

All data for statistical test are analyzed using SPSS and R. All measurements for continuous variables are expressed as mean  $\pm$  standard deviation, and measurements for discrete variables are expressed as percentages. Student's t-test is used for comparative analysis of continuous variables, and  $\chi^2$ -test is used for comparison between two groups for discrete variables. After treatment for myocarditis, recovery of myocardial function and correlation with clinical results were analyzed using paired t test and Kaplan-Meier survival analysis. Predictors of death and factors requiring ECMO treatment were identified through binary logistic regression analysis. Binary logistic regression

analysis requires the occurrence of 10-15 events per independent variable, but in this study, about 30%, or about 270 people, are expected to die, so enough risk factors can be studied. The goodness of fit of the risk prediction model will be tested by C-statistic and Hosmer-Lemeshow tests. In addition, death or re-hospitalization during follow-up will be estimated by the Cox survival analysis method. After checking the fitness of the model by checking Schoenfeld's residual, the hazard of each risk factor is identified. A case of  $P < 0.05$  is considered statistically significant.

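### Only the pooled-variance t-test is named: where groups differ in both size and spread its true error moves off 5% (about 3% to 7% under assumed SD ratios of 0.8 to 1.25), and Welch's test avoids this at almost no cost

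*Combined protocol and SAP*

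**What the plan says.** The SAP section sets the method for continuous variables in one clause: "Student's t-test is used for comparative analysis of continuous variables". The same sentence assigns the chi-squared test to "comparison between two groups for discrete variables", so the t-test is evidently also meant for two independent groups. A P value below 0.05 "is considered statistically significant". No equality-of-variance check, unequal-variance version or alternative test is given.

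The section does not say which groups are compared. Its only group size appears in the events-per-variable argument for logistic regression: "in this study, about 30%, or about 270 people, are expected to die, so enough risk factors can be studied". The Objective points to another possible contrast, the "prognosis of fulminant myocarditis requiring vasopressors or mechanical assist devices", but gives no size for that group.

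The continuous variables include vital signs on admission (Observational data) and echocardiographic measures such as "LVEF, TAPSE, TV s', LV dimension" (Clinical test). The documents give no standard deviation for any of them.

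**The concern.** Student's t-test estimates one common variance from both groups. That is harmless if the groups have the same spread, or if they have the same size. If both differ, the pooled estimate leans towards the larger group's variance, while the true variance of the mean difference depends more on the smaller group's. The standard error is then biased, and a larger sample does not remove the bias. Normality does not protect against it either, so this is a separate matter from skewed laboratory markers.

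Both conditions are plausible here. The plan's expected mortality implies a split of roughly 2.3 to 1 if deaths are compared with survivors. Groups that differ in haemodynamic stability also have no particular reason to share one SD for blood pressure, heart rate or LVEF. What is at stake is the accuracy of P values in the unadjusted group comparisons: too many below 0.05 if the smaller group varies more, too few if the larger group does.

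**Working it through.** **Inputs**
- Deaths: about 270, about 30% (SAP section).
- Total and survivors: not stated. 270 / 0.30 = 900, and 900 − 270 = 630. This is a back-calculation and not an independent check of the plan's figure. It fits the plan's rule of 10 to 15 events per variable: 270 / 15 = 18 and 270 / 10 = 27 predictors.
- Threshold: 0.05 (SAP section). Two-sided is assumed, as the plan does not say.
- Contrast: deaths against survivors, assumed.
- SD ratio k (smaller group over larger group): not in the documents. Assumed range 0.5 to 2.

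**Formulae** (larger group's SD set to 1)
- True variance of the mean difference: Vtrue = k²/270 + 1/630.
- Expected pooled variance: Vpooled = [(269k² + 629)/898] × (1/270 + 1/630).
- True two-sided error: 2 × [1 − Φ(1.96 × √(Vpooled/Vtrue))].

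**Worked case, k = 1.25.** Vtrue = 0.005787 + 0.001587 = 0.007374. Vpooled = 1.1685 × 0.005291 = 0.006183. The square root of their ratio is 0.916, so the pooled standard error is about 8% too small. The effective critical value is 1.96 × 0.916 = 1.795, and the error is 7.3%.

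**Worked case, k = 0.8.** Vtrue = 0.002370 + 0.001587 = 0.003958. Vpooled = 0.8922 × 0.005291 = 0.004720. The square root of the ratio is 1.092, so the standard error is about 9% too large. The effective critical value is 2.141, and the error is 3.2%.

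**Results at 270 against 630**, with a simulation check on normal data (40,000 replicates per ratio):

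| SD ratio | Student, formula | Student, simulated | Welch, simulated |
|---|---|---|---|
| 0.5 | 1.2% | 1.3% | 5.0% |
| 0.67 | 2.2% | 2.2% | 4.9% |
| 0.8 | 3.2% | 3.3% | 5.0% |
| 1.0 | 5.0% | 4.9% | 4.9% |
| 1.25 | 7.3% | 7.4% | 5.0% |
| 1.5 | 9.3% | 9.2% | 5.0% |
| 2.0 | 12.5% | 12.5% | 5.0% |

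**Two boundary checks.** With equal SDs the error at 270 against 630 is 5.0%. With equal groups (450 against 450) the formula gives 5.0% at every ratio. Both kinds of inequality are needed.

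**Cost of Welch when SDs are equal.** Simulated power at a 0.2 SD difference is 0.778 for Welch and 0.780 for Student; at 0.25 SD it is 0.928 against 0.930.

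**The case against.** The strongest reply is that little of this is in the plan itself. The SAP section never says that the t-test compares deaths with survivors, and it states neither 900 nor 630. Fulminant against non-fulminant disease is at least as natural a contrast given the Objective; if that split were near even, the effect would vanish. The SD ratios are assumptions. A short SAP may also use the name Student's t-test generically, and software commonly reports the unequal-variance result as well. Finally, false-positive rates apply only where the true means are equal; where severe patients clearly differ in mean, either test will show it.

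Most of this stands, and it limits the size of the point. It does not remove it. Equal variance is also an assumption, and the plan adopts it without a check. Not naming the groups favours a test that is valid whatever the split. The biased standard error also affects P values for variables whose means do differ, although it changes the conclusion only in borderline cases. If the name was meant generically, a clearer wording is still needed.

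Some stronger readings are tempting but unsupported. A reader might infer that the unequal group sizes alone push the error to 1% or 13%; they do not, because with equal SDs it is 5%. A reader might infer that ECMO comparisons are worse still, but the documents give no ECMO count or proportion. A reader might also infer that distorted t-tests decide which predictors are studied, or that reported confidence intervals will be wrong. The plan describes no t-test screening step and no confidence intervals for mean differences.

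**Conclusion.** The concern holds as a minor point. The plan specifies only the pooled-variance t-test, with no variance check. If the groups are about 270 and 630, the true error is about 3% to 7% for SD ratios of 0.8 to 1.25. It reaches about 1% or 13% only at a twofold SD difference, an extreme that should not be read as the expected case for LVEF or blood pressure. These figures rest on an assumed contrast, a back-calculated total, assumed SD ratios, normal data and a two-sided 5% threshold. A split of 2.3 to 1 is moderate imbalance.

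The reach is narrow: unadjusted two-group comparisons of continuous variables. The main inferences on death, ECMO treatment and re-hospitalization come from logistic and Cox regression, and recovery of function and survival use the paired t-test and Kaplan-Meier analysis. None of these pools the variances of two independent groups. The reason to act is that a better method is available at essentially no cost.

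**What to change.** In the SAP section, replace Student's t-test with *Welch's t-test (unequal variances)* for independent two-group comparisons of approximately symmetric continuous variables. Naming the groups to be compared in the same sentence would remove the remaining ambiguity. The paired t-test needs no change.

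The cost is one phrase. No new data or software is needed: R uses Welch by default, and SPSS prints it beside the pooled result. The power loss when variances are equal is negligible (about 0.2 percentage points at a 0.2 SD difference). No preliminary variance test is needed, since Welch held about 5% at every ratio examined, including equal SDs.

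### Kaplan-Meier is the only curve method named for outcomes that include transplant, LVAD and rehospitalisation, and death is not handled as a competing event

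*Combined protocol and SAP*

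**What the plan says.** The Statistical Analysis Plan (SAP) says that recovery of myocardial function and "correlation with clinical results were analyzed using paired t test and Kaplan-Meier survival analysis". A paired t test suits before-and-after measurements such as echocardiographic values, not events. Kaplan-Meier is therefore the method left for the clinical results.

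The protocol says what that term covers in two places. Under Method, 1) Analysis method, the list is "in hospital mortality, death from any cause, heart transplantation, permanent left ventricular assist device insertion, hospitalization". Under (1) Observational data, item 6, it is "Clinical results: in-hospital mortality, all-cause mortality, heart transplant, left ventricular assist device insertion, re-hospitalization". Each list mixes death with three kinds of non-fatal event.

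On mortality, the SAP says that "about 30%, or about 270 people, are expected to die". It also says that "death or re-hospitalization during follow-up will be estimated by the Cox survival analysis method", without stating whether that is one composite endpoint or two separate ones.

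The SAP does not say which clinical results get a Kaplan-Meier curve, how a death before a non-fatal event is treated, or when time starts for rehospitalisation. It names no cumulative incidence function or other competing-risk method.

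**The concern.** When Kaplan-Meier is run on a single non-fatal event, a patient who dies without the event is usually entered as censored. The estimator then treats that patient as someone who could still be transplanted, receive an LVAD or be readmitted later. The complement of the curve describes a hypothetical population in which nobody dies. Read as the proportion of patients who actually have the event, it is too high.

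The mortality the SAP expects is large enough for this to matter. The excess also grows with mortality. The Background says that fulminant disease has the poorer prognosis, and the Objective centres on the outcome of fulminant patients. Two groups with the same true incidence of transplant could therefore show different Kaplan-Meier estimates only because more patients die in one of them.

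**Working it through.** **The plan's own figure.** 270 / 0.30 = 900 patients. The documents do not state a total, so 270 deaths are consistent with about 900 patients but cannot be reproduced independently. It is not stated whether the 30% are in-hospital deaths or deaths over all follow-up.

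**Inputs.**
- *d*, the proportion who die before the non-fatal event: 10%, 20% and 30%. The 30% is the SAP's expected mortality, with every death taken to come first. The lower values are assumptions, because deaths after the event do not compete with it.
- *c*, the true cumulative incidence of the non-fatal event: 5% to 30%. This is an assumed range, as the documents give no rate for transplant, LVAD or rehospitalisation.

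**Formula.** Let T = c + d. With constant proportional cause-specific hazards, the total cumulative hazard is -ln(1 - T), and the event contributes the share c/T. With deaths censored:

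1 - KM = 1 - (1 - T)^(c/T)

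Example: c = 0.20 and d = 0.30 give T = 0.50 and c/T = 0.40, so 1 - 0.50^0.40 = 0.242.

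| True incidence | 1 - KM, d = 10% | 1 - KM, d = 20% | 1 - KM, d = 30% |
|---|---|---|---|
| 5% | 5.3% | 5.6% | 6.0% |
| 10% | 10.6% | 11.2% | 12.0% |
| 20% | 21.2% | 22.5% | 24.2% |
| 30% | 31.8% | 34.0% | 36.8% |
| Relative excess | about 6% | 12-13% | 19.4-22.5% |

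At d = 30% the absolute excess runs from about 1 point (5% true) to about 7 points (30% true).

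**Simulation check.** With 400,000 simulated patients, d = 30% and c = 20%, the true incidence was 20.1% and 1 - KM was 24.3%. For the composite of death or the event, 1 - KM was 50.1% against a true 50.1%, so there was no bias.

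**Timing of deaths.** If all 30% of deaths came before any non-fatal event, 1 - KM = c / (1 - d). Then 5%, 10%, 20% and 30% become 7.1%, 14.3%, 28.6% and 42.9%, a relative excess of 1/0.70 - 1 = 43%.

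**Two groups with equal true incidence.** Take c = 20% in both groups, with assumed values of d:
- d = 5%: 1 - 0.75^(0.20/0.25) = 20.6%
- d = 30%: 24.2%

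The gap of 3.6 points comes only from the difference in mortality. In a group with d = 40%, the estimate would be 1 - 0.40^(0.20/0.60) = 26.3%.

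**The case against.** A reader might infer that the plan will censor deaths and that its reported rates of transplant, LVAD and rehospitalisation will be too high. The documents do not support that. They never say that each non-fatal result gets its own curve, and they give no censoring rule at all. Other readings are open:

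- The SAP expresses discrete variables as percentages and compares them by chi-square. Transplant and LVAD could be reported that way, and crude percentages do not carry this bias.
- The Cox endpoint can be read as a composite that includes death, which has no competing death.
- Kaplan-Meier is suitable for all-cause death, which is on the same list.

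A reader might also infer that any comparison of fulminant with non-fulminant patients would be invalid. That too goes beyond the text. The SAP specifies no such Kaplan-Meier comparison. A log-rank test or Cox model with deaths censored compares cause-specific hazards, which is a legitimate estimand. The bias belongs to reading 1 - KM as an absolute incidence.

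Finally, 30% is an upper value of *d* for the whole cohort. For rehospitalisation counted from discharge, in-hospital deaths drop out altogether.

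All of this stands, and it makes the point conditional. It does not remove it. The composite reading reaches only rehospitalisation. For transplant and LVAD, Kaplan-Meier is the only time-to-event method linked to them, and an analyst who applied it to each listed outcome would be following the SAP as written.

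**Conclusion.** The concern holds in conditional form. The SAP links Kaplan-Meier to a set of outcomes that includes three kinds of non-fatal event and does not say how death is handled. If those events are analysed singly with deaths censored, their cumulative incidence is overstated. The excess is about 6% in relative terms when 10% die first and rises to 19.4-22.5% when 30% do. It is larger in a group with higher mortality.

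These sizes rest on constant proportional hazards and an assumed true incidence of 5-30%. Earlier deaths would increase the excess, up to 43% if all 30% came first. Deaths after the event would reduce it. Mortality results and composites that include death are not affected. The point is worth correcting because the SAP's named method, applied to its own list of outcomes, can give biased rates and a suitable alternative is readily available.

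**What to change.** In the Statistical Analysis Plan (SAP):

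1. Name each time-to-event endpoint. Use Kaplan-Meier only for all-cause death and for composites that include death.
2. For transplant, LVAD and rehospitalisation as single endpoints, report the Aalen-Johansen cumulative incidence function with death as the competing event.
3. State whether the Cox endpoint of death or rehospitalisation is a composite.
4. Start rehospitalisation time at discharge, among patients discharged alive.
5. For group comparisons, use either cause-specific hazards (log-rank or Cox) or Gray's test, and state which estimand is meant.

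The cost is SAP wording and standard code in R, which the SAP already names. Event and death dates are needed, but Kaplan-Meier and Cox analyses of the same outcomes need them too. The downside is slightly more analysis work and lower reported rates for the non-fatal events than 1 - KM would give.

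### Does the logistic model for death need changing because the SAP does not say which death, or by when?

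*Combined protocol and SAP*

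**What the plan says.** The Statistical Analysis Plan states: "Predictors of death and factors requiring ECMO treatment were identified through binary logistic regression analysis". It then applies a rule of 10 to 15 events per predictor and expects about 30% of patients, about 270, to die. Neither the model outcome nor the 270 is tied to a type of death or a time point. As a further step, the SAP assigns death or readmission over follow-up to Cox regression with a check of Schoenfeld residuals. It also plans Kaplan-Meier analysis of clinical results.

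The protocol keeps two death outcomes apart. Method, 1) Analysis method, lists "in hospital mortality, death from any cause" among the clinical results. The clinical-results item under (1) Observational data lists "in-hospital mortality, all-cause mortality, heart transplant, left ventricular assist device insertion, re-hospitalization".

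Patients were diagnosed "from January 2004 to December 2021 at 6 domestic institutions" (Design). Outcomes "should be confirmed prior to the clinical trial approval date", which is one administrative limit for everyone and not a window per patient.

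**The concern.** A binary outcome needs a definition, and here there are two candidates. The choice could matter in two ways.

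- **All-cause death up to the closing date.** A survivor admitted in late 2021 counts as a full non-event after a short observation, and one admitted in 2004 only after many years. A factor with no effect on death, but whose frequency changed between 2004 and 2021, could then appear to predict death.
- **In-hospital death.** That bias disappears. But if the 270 includes deaths after discharge, the model has fewer events than the SAP implies and supports fewer predictors.

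**Working it through.** **1. The SAP's own figure.** The total sample size is not stated. Back-calculation gives 270 / 0.30 = 900. At the SAP's rule, 270 / 15 = 18 and 270 / 10 = 27, so 18 to 27 predictors. This arithmetic is the same for either type of death, so it cannot show which is meant.

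**2. What the wording suggests.** The logistic sentence pairs death with the need for ECMO, an event of the acute phase. The SAP then adds Cox regression for events over follow-up. The 270 comes directly after the logistic sentence, so its plainest sense is events for that model. Together these favour in-hospital death. This is inference, since no sentence says so.

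**3. In-hospital reading.** The outcome is known at discharge, so length of follow-up plays no part. If the 30% is the in-hospital rate, the 270 events and 18 to 27 predictors hold as written. If the 30% is all-cause, the in-hospital count is 900 × e for an assumed in-hospital rate e:

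| e (assumed) | Events | Predictors at 15 to 10 events each |
|---|---|---|
| 10% | 90 | 6 to 9 |
| 15% | 135 | 9 to 13 |
| 20% | 180 | 12 to 18 |
| 25% | 225 | 15 to 22 |
| 30% | 270 | 18 to 27 |

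The SAP states no number of predictors, so no row shows a shortfall.

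**4. All-cause reading with no fixed window.** Assumptions: uniform entry over 18 years, closing at the end of the window, in-hospital death probability p0, a constant hazard λ afterwards, and no loss to follow-up. Then P(t) = p0 + (1 − p0)(1 − exp(−λt)), with λ solved so that average mortality is 30%. For p0 = 10%, λ = 0.0292 per year. Mean mortality is 0.391 for entrants in the first nine years and 0.209 for those in the last nine. The odds ratio is (0.391/0.609) / (0.209/0.791), or 2.44 with unrounded inputs, from follow-up time alone. For p0 = 0, 15, 20 and 25% it is 3.75, 1.97, 1.58 and 1.26. At p0 = 30% no later deaths remain, so it is 1.

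**5. What that would do to a null factor.** Cohorts of 900 were simulated with closing six months after the last admission, constant later hazard and a factor rising from 10% to 50% prevalence over the period. The test was a two-sided 5% Wald test of the log odds ratio.

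| In-hospital death (assumed) | Follow-up (assumed) | False-positive rate |
|---|---|---|
| 0% | no loss | 66% |
| 5% | no loss | 52% |
| 10% | no loss | 37.4% |
| 20% | no loss | 13.1% |
| 25% | no loss | 7.2% |
| 30% | no loss | about 5% |
| 10% | median time to loss 3 years | 9.7% |
| 20% | median time to loss 3 years | 6.7% |

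With the smaller drift of 10% to 30%, 10% in-hospital death and no loss, the rate is 15.0%. The documents give no in-hospital rate, loss rate, closing date or factor frequency by year, so they do not favour any row.

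**The case for a change.** The strongest case for a change is that the omission is plain from the text, the fix is a few words, and naming the outcome beforehand prevents a choice between two death definitions after the results are seen. The data lists hold 31 patient, laboratory and imaging items (6 + 5 + 8 + 10 + 2), more than the 27 predictors that 270 deaths support at most, so the event count limits model size. The Cox sentence may describe one composite outcome, which would leave all-cause death without a regression of its own.

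The omission stands, and so does the point that in-hospital death is inferred. The rest carries less weight:

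- The 31 items are a list of data to collect. Nothing says that all of them enter one model.
- If the Cox sentence means two outcomes, Cox regression for death is already planned. If it means a composite, Kaplan-Meier analysis of clinical results is still planned.
- The Objective is to describe characteristics, treatment results and prognosis. No confirmatory test depends on which death this model uses.
- The bias is not inherent in all-cause death. A fixed, fully observed window would avoid it, and the SAP does not rule one out.

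**Conclusion.** The outcome of the logistic model and the type of death behind the 270 are not stated, but this is missing detail and not a demonstrated error. On the likelier reading, in-hospital death, bias from unequal follow-up is absent, and if 30% is the in-hospital rate the SAP's 270 events and 18 to 27 predictors stand. An analyst who has both death outcomes recorded, and a Cox model set aside for follow-up, would ordinarily use in-hospital death for the logistic model and would have to name it when reporting.

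Material harm requires three things together: all-cause death with no fixed, fully observed window; a factor whose frequency changed markedly over the 18 years; and follow-up long enough for the difference to show. The false-positive rates of about 5% to 66% describe those assumptions and not this study. No change to the plan follows.
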